5 SAMPLE SIZE AND POWER

This study is descriptive in nature and is not powered to show statistically significant treatment differences for any outcome measure. A sample of approximately 70 subjects, randomized in a 1:1 ratio to the belatacept + EVL and TAC + MMF groups, is planned.

If the true probability of CSBPAR in the belatacept + EVL treatment group is 3.8%, a sample size of 35 subjects allows the estimation of the population proportion (π) with a 95% CI[†] of 0.2% to 16.4% around the observed proportion of CSBPAR. If the rate is 3%, in the TAC +MMF treatment group, then the 95% CI[†] around the estimate would be 0.1% to 15.1%, for lower and upper limits, respectively.

For the secondary endpoint of assessing the difference in the incidence of CSBPAR at 6 months post-transplantation between the TAC + MMF and belatacept + EVL groups, respectively, with 35 subjects per treatment group, if the observed incidences of CSBPAR (conservatively based on study IM103034) are 3% and 3.8%, the 2-sided 95% confidence interval (CI)* of the differences between the observed incidence rates can be summarized as in Table 5-1:

Table 5-1: Confidence Intervals* for the Difference between Two Proportions

Difference of Treatments (assumed proportions)	Lower 95% Confidence Limit	Upper 95% Confidence Limit	Half Width
TAC + MMF (3%)			
vs.	-13.2%	11.3%	12.25%
Bela + EVL (3.8%)			

[†] Confidence Interval Method: Clopper-Pearson

* Confidence Interval Method Score (Wilson)

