7.2 General Methods

All analyses of efficacy and safety endpoints will be summarized descriptively by the two treatment groups. No statistical tests will be performed.

Randomization to the study will be stratified by site only. Any within-treatment confidence interval (CI) for the proportion analyses will be computed using normal approximation, if the number of the events in that treatment group is at least 5. Otherwise, a CI calculated using an exact method will be provided. Any between-treatment CI for the proportion difference analyses will also be computed using normal approximation, if the number of the events in each individual treatment group is at least 5. Otherwise, a CI using an exact method will be provided.

For time to event analyses, if a patient does not experience an event, the censoring will be done at the last follow-up date if the subject discontinues prematurely; otherwise, censoring will be

done at the last dose date if the subject completed the 24 month-treatment period, unless specified otherwise.

The following table provides an overview of the primary and key secondary analyses to be performed.

Table 7.2-1: Overview of Primary and Key Secondary Analyses

Measure of Interest	Analysis Method
Proportion of subjects who experience a CSBPAR at 6, 12 and 24 months post-transplant	Point estimate of the proportion and 95% CI [*] within each treatment group at 6 months.
Difference in the incidence of CSBPAR between arms, at 6, 12 and 24 months post-transplant	Point estimate and 95% CI [†] for the difference between the two arms
Time to first CSBPAR	Kaplan-Meier (KM) estimates of survival functions. Hazard Ratio and 95% CI [§]
Proportion of Subjects who survive with a functioning graft at 24 months post-transplant	Point estimate of the proportion and 95% CI [*] within each treatment group at 24 months (to be produced if there are at least 5 subjects across treatment groups who died or experienced graft loss)
Time to death or graft loss	KM estimate of subject and graft survival Hazard Ratio and 95%CI [§] (to be produced if there are at least 5 subjects across treatment groups who died or experienced graft loss)

* Confidence Interval Formula: Exact (Clopper-Pearson)

† Confidence Interval Method: Score (Wilson)

§ Using Cox Proportional Hazard model

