7.6.2.3 Renal Function

The following table provides a summary/overview of the analysis performed.

Table 7.6.2.3-1: Overview of Analysis: Renal Function

Renal Function variable	Analysis	Time points for analysis
cGFR using MDRD formula	Descriptive summary of absolute values for each Treatment group	Month 3, 6, 12, 24
	Descriptive summary of change from Month 3 values for each Treatment group	Month 6, 12, 24
	Fixed Effects repeated measure model using Time and Treatment as class variables and Month 3 cGFR as a covariate	Month 6, 12, 24
	Mixed effects using Time as random variable and Treatment as class variable. Analysis on absolute cGFR value using Month 3 cGFR as a covariate	Month 6, 12, 24
Urine protein/ creatinine ratio (U _{PR} /CR)	Descriptive summary of absolute values for each treatment group	Month 3, 6, 12, 24
	Descriptive summary of change from Month 3 values for each Treatment group	Month 6, 12, 24
	Fixed Effects repeated measure model using Time and Treatment as class variables and Month 3 cGFR as a covariate	Month 6, 12, 24

cGFR

Calculated GFR at Months 3, 6, 12, and 24 and change in cGFR from Month 3 to Months 6, 12 and 24, respectively, will be descriptively summarized.

A linear mixed effects model will be used to analyze changes from Month 3 cGFR. The linear mixed model for repeated measures with terms of Month 3 cGFR values, treatment, month, and interaction of treatment by month. The variable month will be categorical. The unstructured (UN) covariance structure will be assumed. If computation convergence becomes an issue, the compound symmetric (CS) covariance structure will be used. For each time point, the difference between treatment arms will be calculated along with the corresponding 95% confidence intervals.

Population-mean slopes will be estimated for each treatment group. In addition, the 95% confidence intervals will also be obtained for each mean slope. Intercepts will be summarized in the same manner. This analysis will be based on a linear mixed model including terms for treatment, Month 3 cGFR, treatment-by-month interaction as well as month (continuous covariate) as fixed effects. The model will also include a random intercept and slope for month. Unstructured covariance structure will be used.

For all of the analyses above, for any subject who has one or more missing values for cGFR due to a graft loss or death, the missing values will be imputed as “zero”.

Urine Protein/Creatinine Ratio

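### If the unstructured cGFR model fails to converge, the SAP's only fallback forces one variance on all visits, and the Month 24 between-arm interval can then be too narrow

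*SAP*

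**What the plan says.** SAP 7.6.2.3 fits a linear mixed model for repeated measures to change from Month 3 in cGFR. Its terms are the Month 3 value, treatment, categorical month and treatment by month. On covariance it says: "The unstructured (UN) covariance structure will be assumed". The contingency follows at once: "If computation convergence becomes an issue, the compound symmetric (CS) covariance structure will be used". The output is stated as: "For each time point, the difference between treatment arms will be calculated along with the corresponding 95% confidence intervals". The UPCR paragraph repeats the covariance sentence, the fallback and the intervals. Neither paragraph names an intermediate structure, a robust standard error or a degrees-of-freedom method.

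Two other statements in the cGFR text bear on how the variance behaves over time:

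- A separate slope analysis, with month continuous: "The model will also include a random intercept and slope for month".
- A rule covering all the cGFR analyses: "for any subject who has one or more missing values for cGFR due to a graft loss or death, the missing values will be imputed". The value put in is zero. SAP 8.3 repeats this for cGFR and leaves other missing values missing.

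SAP 5 gives the scale and purpose: "A sample of approximately 70 subjects, randomized in a 1:1 ratio", and "This study is descriptive in nature and is not powered to show statistically significant treatment differences for any outcome measure". SAP 7.2 adds: "No statistical tests will be performed".

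**The concern.** Unstructured covariance gives each of the three visits its own variance. Homogeneous compound symmetry gives them one variance and one correlation. If the true variance rises from Month 6 to Month 24, the pooled value is too large for Month 6 and too small for Month 24, and the interval widths follow.

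The SAP's own cGFR rules make a rising variance plausible. Subject-specific slopes spread subjects apart as time passes. Graft loss and death are permanent, so zeros can only accumulate. Each one arising after Month 3 enters as a change equal to minus the subject's Month 3 value. (A graft lost before Month 3 scores zero at every visit, so its change is zero throughout and adds no growth.)

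The label on the Month 24 interval is at stake. With no tests planned, the interval is the inferential statement, and these are the only between-arm cGFR intervals that the section names. A fallback is also the part of a plan that should be settled before the data are seen.

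**Working it through.** **1. The plan's own figures.** The SAP gives no precision figure for cGFR or UPCR. Its only ones concern acute rejection, and they reproduce at 35 per arm: the difference of 3% and 3.8% has a Wilson-score interval of -13.17% to 11.32% (stated -13.2% to 11.3%), and the Clopper-Pearson intervals are 0.21% to 16.37% and 0.09% to 15.14% (stated 0.2% to 16.4% and 0.1% to 15.1%).

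**2. Inputs.** From the SAP: 35 per arm; visits at Months 6, 12 and 24; the model terms; the zero rule. Assumed, because the documents give nothing: Month 3 mean 60, between-subject SD 15, measurement SD 7 or 8, slope SD 0 to 6 mL/min/1.73 m² per year (4 in step 4), losses of 0% to 10% by Month 24, other dropout 15%, no true treatment difference. Standard errors are taken from the fitted covariance, since the SAP names no other method. For scale, 3% of 70 is about 2 subjects and 7% is about 5. Five is the count at which SAP 7.1 produces survival summaries, but that is a reporting threshold and not an expected rate.

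**3. Formula.** With near-complete data, the ratio of the compound-symmetry to the unstructured standard error at visit t is √(mean of the three visit variances ÷ variance at t), with variances conditional on Month 3. Approximate coverage is 2Φ(1.96 × ratio) − 1.

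**4. Slopes alone.** With between-subject SD 15, measurement SD 7, slope SD 4 per year independent of the intercept, and τ in years from Month 3 (0.25, 0.75, 1.75):

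- V = 225 + 49 − 225²/274 + 16τ² = 89.24 + 16τ², giving 90.24, 98.24 and 138.24, with mean 108.91.
- Month 24: √(108.91/138.24) = 0.888, coverage about 91.8%.
- Month 6: √(108.91/90.24) = 1.099, coverage about 96.9%.

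**5. Zeros alone.** With conditional SD 12, mean 60, and a fraction p scored zero, V = (1 − p)·144 + p(1 − p)·3600.

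- For p = 0, 0.014 and 0.029, V = 144, 191.7 and 241.2, with mean 192.3.
- Month 24: √(192.3/241.2) = 0.893, coverage about 92.0%. Month 6: √(192.3/144) = 1.156.
- If p is 0.05 at every visit, all three ratios are 1.00. It is accumulation that does the damage.

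**6. Simulation of the SAP model** (REML, 70 subjects, measurement SD 8, 400 runs, Monte Carlo error about 1 to 2 points). UN is unstructured and CS is compound symmetry.

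| Slope SD per year | Zeros by Month 24 | Month 24 mean SE, UN / CS | Ratio | Month 24 coverage, CS (UN) | Month 6 ratio | Month 6 coverage, CS |
|---|---|---|---|---|---|---|
| 0 | 0% | 2.72 / 2.74 | 1.01 | 93.8% (92.0%) | 1.00 | 94.5% |
| 3 | 0% | 3.04 / 2.85 | 0.94 | 92.5% (93.5%) | 1.04 | 96.2% |
| 6 | 0% | 3.81 / 3.18 | 0.83 | 92.0% (94.8%) | 1.15 | 98.5% |
| 0 | 3% | 3.85 / 3.35 | 0.87 | 89.5% (94.8%) | 1.16 | 96.8% |
| 3 | 3% | 4.03 / 3.42 | 0.85 | 89.8% (94.2%) | 1.18 | 98.2% |
| 3 | 7% | 5.07 / 4.07 | 0.80 | 86.2% (94.8%) | 1.31 | 99.5% |
| 6 | 10% | 6.00 / 4.63 | 0.77 | 84.8% (95.2%) | 1.41 | 99.5% |

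The unstructured model converged in every data set.

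**7. Does a variance per visit repair it?** With 600 runs at slope SD 3 and losses of 0%, 3% and 7%, Month 24 coverage under heterogeneous compound symmetry was 94.5%, 95.0% and 96.2%. Homogeneous compound symmetry gave 91.8%, 90.5% and 89.7%; unstructured gave 94.5%, 95.3% and 96.2%.

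**8. Do sandwich errors repair it?** In a separate simulation (1,500 runs, residual SD 7, no dropout other than losses scored zero), homogeneous compound symmetry with sandwich errors left 4.2% to 5.3% of Month 24 intervals excluding zero under no effect. With standard errors from the fitted covariance, the figure was 6.6% at slope SD 3 without losses, 10.1% at slope SD 5 without losses, and 9.3% at slope SD 3 with one loss per arm on average.

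**9. UPCR.** No random slope or zero rule is stated. With illustrative SDs of 0.4, 0.5 and 0.7, the Month 24 ratio is √(0.30/0.49) = 0.78. With equal SDs it is 1.00. With the order reversed it is √(0.30/0.16) = 1.37.

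**The case against.** The strongest reply is that the trigger is remote. Three visits need only six covariance parameters, there are about 70 subjects, and no simulated unstructured fit failed. That stands, although real data are less regular than simulated data. It keeps the severity low without making the stated rule a sound one.

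The second reply is that the study is descriptive, unpowered and without tests, and that this is a secondary endpoint. The visit summaries and the per-arm slopes with their intervals do not depend on the fallback. This also stands and limits the consequence. It does not excuse a 95% interval that covers less often than its label says.

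Three stronger readings are tempting, and the documents do not support them:

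- *The fallback contradicts the SAP's own assumptions.* The slope model is a separate analysis with its own covariance. A random slope permits growing variance without asserting that it is large, and the first-choice structure accommodates it fully. The fallback is a poor fit to the implied pattern, not a contradiction.
- *The UPCR interval is too narrow as well.* The random slope and the zero rule are cGFR rules, so the direction of any UPCR error is unknown.
- *Falling back is enough to spoil the interval.* The variance must also rise. With no slope variation and no accumulating zeros, the two structures agree.

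**Conclusion.** The point holds for cGFR as a conditional, low-severity weakness. Two things must happen together: the unstructured model fails, and the variance of change rises by Month 24. The Month 24 standard error is then about 6% to 23% too small, coverage is about 85% to 92%, and the Month 6 interval is up to about 41% too wide.

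These sizes assume slope SDs of 3 to 6 mL/min/1.73 m² per year and/or 3% to 10% losses by Month 24, and standard errors taken from the fitted covariance. None of these is given in the documents. At the mild end, slope SD 3 with no losses, the effect on coverage is barely distinguishable from simulation error in a single run. For UPCR only the equal-variance restriction can be said to be shared.

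**What to change.** In the cGFR paragraph of SAP 7.6.2.3, replace the fallback sentence with:

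*If the unstructured model does not converge, heterogeneous compound symmetry (a separate variance per visit) will be used; if homogeneous compound symmetry is still needed, 95% CIs will use the empirical (sandwich) variance estimator.*

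Use the same sentence in the UPCR paragraph as a safeguard.

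One intermediate step is enough. Heterogeneous compound symmetry has four parameters, against six for unstructured and two for the homogeneous form. Heterogeneous Toeplitz would have five, which saves only one over unstructured. An autoregressive structure by visit order would treat the 6-month gap (Months 6 to 12) and the 12-month gap (Months 12 to 24) as equal.

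The cost is one sentence in two paragraphs and one program option, with no new data. The price is two more covariance parameters than homogeneous compound symmetry and, if the last step is reached, slightly more variable standard errors at 35 per arm.

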### **Renal Function**

- Absolute (mean and median) cGFR values at 3, 6, 12 and 24 months post-transplant, as determined from the 4-variable Modification of Diet in Renal Disease (MDRD) formula;
- The mean change from Month 3 cGFR at 3, 6, 12 and 24 months post-transplant;
- Slope of the change in cGFR from Month 3 to Months 6, 12 and 24 post-transplant;
- Urine protein to creatinine ratio ( $U_{Pr/Cr}$ ) at 3, 6, 12 and 24 months post-transplant.

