#### **8.4.2.3    *Renal Function***

Calculated GFR at Months 3, 6, 12, and 24 and change in cGFR from Month 3 to Months 6, 12 and 24, respectively, will be descriptively summarized. For a subject who has one or more missing values for cGFR due to a graft loss or death, the missing values will be imputed as “zero”.

A linear mixed effects model will be used to analyze changes from Month 3 cGFR. Details of the analyses will be available in the Statistical Analysis Plan.

Population-mean slopes will be estimated for each treatment group. In addition, the 95% confidence intervals will also be obtained for each mean slope. Intercepts will be summarized in the same manner.

In addition, urinary protein to creatinine ratios, to be obtained from single-voided urine specimens at 3, 6, 12 and 24 months post-transplant, will be descriptively summarized.

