8.3 Missing Data Handling

The following conventions will be followed while handling missing data. Only the relevant endpoints along with the specifics of the convention are included in this section.

Subject Survival and Graft Survival

Any subject (either randomized to belatacept or CNI) with unknown subject and graft survival status at Month 12 or Month 24, that is, whose last known follow-up date occurred prior to Day 334 or Day 698, respectively, will be considered as having experienced an event of graft loss or death, if at least one of the following criteria have been met during their documented period of follow-up post-randomization:

- Subject experienced at least one episode of BPAR at the time of, or prior to the last follow-up date.
- Subject was diagnosed as having PTLD at the time of, or prior to the last follow-up date.
- Subject's reason for discontinuation of study medication was lack of efficacy.
- A diagnosis of biopsy confirmed Polyomavirus associated nephropathy was reported as an adverse event before discontinuation.
- Subject's last calculated GFR (4-variable MDRD equation) was $< 15\text{mL}/\text{min}/1.73\text{m}^2$.

The remaining subjects with unknown patient and/or graft survival status at Months 12 or 24 (those who do not meet any of the above criteria) will be considered missing and not be included in the analyses or listing of the death and graft loss. For example, a patient with unknown status of the graft function and patient survival, and with no records of the above mentioned criteria, will not be considered in the numerator or denominator, while computing the percentage of death or graft loss.

Acute Rejection

Any acute rejection-free subject who is not followed-up through the entire event-counting period due to any reason will be considered as having no acute rejection during that period.

Renal Function

Missing cGFR values due to death or graft loss will be imputed with value of 0 and all other missing values will remain missing.

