8.4 Day Ranges for Analysis Time Points

Subjects do not always adhere strictly to the visit schedule timing in the protocol. Therefore the designation of the visits/months during the study will be based on the day of evaluation relative to day 1 of the trial (first dose date = study day 1) rather than the nominal visit/month recorded in the case report form (CRF).

The following rules apply to the derived visits depending on the specific endpoint. All endpoints analyzed over time will follow the analysis windowing specified in Table 8.4-1.

Table 8.4-1: Day Ranges for Analysis Time Points

At Month	Target Day	Day Range
1	28	1-56
3	84	57-112
6	168	141-196
9	252	225-280
12	364	337-392
15	448	421-476
18	532	505-560
21	616	589-644
24	728	701-756

Note: If a subject has more than one measurement recorded within the window for that time point, the measurement closest to the target day for that time point will be used. In any case in which both observations are equidistant from the target day, the later measurement will be used.

If data are collected at Month 2 (Week 8) then the day ranges are the following:

At Month	Target Day	Day Range
1	28	1-42
2	56	43-70
3	84	71-112

At Month	Target Day	Day Range
...		

In addition, the analyses for subject and graft survival, acute rejection related endpoints, NODAT and adverse events will follow the windowing below:

- Month 6: Defined as Day 1 to Day 168.
- Month 12: Defined as Day 1 to Day 364.
- Month 24: Defined as Day 1 to Day 728.

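### The zero rule for cGFR lost to graft failure or death does not exempt Month 3, so a loss before Month 3 is summarised as no change and a flat slope

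*SAP*

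**What the plan says.** SAP 7.6.2.3 summarises cGFR at Months 3, 6, 12 and 24 and its change from Month 3 to the later visits. It then specifies two models.

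- A repeated-measures model of change from Month 3, with Month 3 cGFR, treatment, month and treatment-by-month. It gives the only between-arm cGFR contrast: "For each time point, the difference between treatment arms will be calculated along with the corresponding 95% confidence intervals".
- A random intercept and slope model, described in Table 7.6.2.3-1 as "Mixed effects using Time as random variable and Treatment as class variable. Analysis on absolute cGFR value using Month 3 cGFR as a covariate", with responses at Months 6, 12 and 24. It is reported by arm: "Population-mean slopes will be estimated for each treatment group".

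After these comes a rule that fills gaps with zero: "For all of the analyses above, for any subject who has one or more missing values for cGFR due to a graft loss or death". SAP 8.3 repeats it ("Missing cGFR values due to death or graft loss will be imputed with value of 0"), with other missing values left missing, and so does Protocol 8.4.2.3 ("For a subject who has one or more missing values for cGFR due to a graft loss or death"). None of the three says what happens when the missing value is Month 3 itself. The ITT definition in SAP 6.2 does not require a subject to reach Month 3.

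Visits are assigned by study day: "the designation of the visits/months during the study will be based on the day of evaluation relative to day 1 of the trial". The Month 3 window is Day 57 to 112, or Day 71 to 112 where Month 2 data are collected.

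**The concern.** Zero imputation is evidently meant to make a lost graft count as a failure. At visits after Month 3 it does so. At Month 3 the zero becomes the reference value, and the later zeros are subtracted from it. In the by-arm change and slope summaries the failure then cannot be told apart from a graft that held its function.

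The size of the penalty also depends on timing. A loss shortly after an observed Month 3 value counts in full in change; the same loss shortly before counts as nothing. The model contrast is left without a clear meaning. It is neither the full effect of losing the graft nor the effect among grafts functioning at Month 3.

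The trial is open-label, so if a case occurred, a later decision on how to handle it would be taken with its arm known.

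**Working it through.** The documents give no cGFR mean, SD, slope or correlation, so there is no planned figure to reproduce. Everything below except the arm size of 35 (SAP 5) is an assumption.

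**1. The rule applied to single subjects** (functioning graft at 55, no decline; change is the value at Months 6, 12 and 24 minus the Month 3 value)

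| Subject | Months 3, 6, 12, 24 | Change at 6, 12, 24 |
|---|---|---|
| Stable graft | 55, 55, 55, 55 | 0, 0, 0 |
| Lost before a Month 3 value | 0, 0, 0, 0 | 0, 0, 0 |
| Lost just after Month 3 | 55, 0, 0, 0 | -55, -55, -55 |

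The first two rows also share a slope of 0.

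**2. False gain in the arm's own summaries.** Let survivors decline by d per year. Month 24 is 1.75 years after Month 3, and k of 35 subjects are early losses.

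- Mean Month 24 change moves up by d × 1.75 × k/35. With d = 2 and k = 3 this is 2 × 1.75 × 3/35 = +0.30 mL/min. It is 0 if d = 0 and +0.60 if d = 4.
- Mean slope moves up by d × k/35 = 2 × 3/35 = +0.17 per year (0 to +0.34 for d from 0 to 4).

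**3. The between-arm model.** Because Month 3 cGFR is a covariate, modelling change or absolute cGFR gives the same treatment difference. If change = b × Month 3 + other terms, then absolute = (1 + b) × Month 3 + the same other terms. The early loss therefore enters as the point (0,0).

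Survivors average 55 at Month 3 and 55 - 2 × 1.75 = 51.5 at Month 24, so with k early losses in one arm:

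- absolute-scale shift = -51.5 × k/35, which is -4.41 for k = 3;
- shift in the adjusted contrast ≈ -(k/35) × [51.5 - 55 × (1 + b)].

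The zeros also pull b. At SD 15 and correlation 0.6 it goes from about -0.41 to about -0.27. Then 55 × 0.73 = 40.15, 51.5 - 40.15 = 11.35, and 11.35 × 3/35 gives a shift of -0.97.

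**4. Simulation of the SAP model** (unstructured covariance, the same data with and without losses, three losses in one arm; Month 24 shift in mL/min)

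| Correlation | 0.6 | 0.7 | 0.8 | 0.9 |
|---|---|---|---|---|
| SD 15 | -0.96 | -0.66 | -0.36 | -0.06 |
| SD 20 | -1.17 | -0.82 | -0.46 | -0.10 |

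- The absolute-scale shift is -4.40 to -4.42, so 1% to 27% is retained.
- The same three losses just after Month 3 shift the contrast by -4.40 to -4.41.
- Leaving the early losses out gives 0.00 to +0.02.
- One early loss gives -0.04 to -0.47, against about -1.5 on the absolute scale.
- The standard error of the contrast is 1.5 to 3.8.

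**5. Wider grid.** Means 45, 55, 65; declines 0, 2, 4 per year; SD 15, 20; correlation 0.6, 0.9 (36 settings), three early losses. The shift runs from -1.59 to +0.21, against -3.30 to -5.63 on the absolute scale. It becomes positive only with a decline of 4 per year and high correlation.

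**The case against.** A reader might infer that the between-arm contrast treats an early loss as stable function, or rewards the arm that suffers it. The documents do not support that. With Month 3 as covariate, the loss has the lowest possible response at the lowest possible covariate value. In the main illustration the shift goes against the arm with losses in every setting. The wrong sign needs inputs the documents do not give, and then reaches only about 0.2 mL/min. The loss is heavily diluted; it is not turned into a benefit.

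Four further objections have weight.

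- **Few subjects can be affected.** Under Protocol 5.3.12, dialysis-defined loss needs at least 56 days, so many such subjects could have a value inside the Month 3 window. What remains is mainly early death, nephrectomy, re-transplantation or dialysis from the first days. The documents forecast no such losses, and the eligibility criteria exclude higher-risk recipients and extended criteria kidneys.
- **The losses are not hidden.** Absolute cGFR with zeros is summarised by arm. SAP 7.6.2.1 lists every death and graft loss without a minimum count. Disposition (SAP 7.4.1) and safety (SAP 7.7) report them too.
- **The endpoint itself is part of the cause.** Protocol 8.3.2 asks for "The mean change from Month 3 cGFR at 3, 6, 12 and 24 months post-transplant", and a change from Month 3 cannot show a loss that came before it. Excluding early losses removes them from the contrast altogether.
- **The study is descriptive**, without tests, and cGFR is secondary. A false gain of 0.3 mL/min is a small fraction of the standard error of the arm's mean change.

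These points limit the importance of the defect. They do not make change 0 a correct score for a failed graft, and none of the other displays repairs the change and slope results.

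**Conclusion.** The point holds and is minor. Three places state the zero rule and none exempts Month 3. A subject whose Month 3 value is missing through earlier loss or death gets change 0 in the by-arm summaries and a flat line in the slope model. In the model contrast the same subject distorts the covariate coefficient and leaves only a small part of the loss visible.

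The sizes in the brief assume all losses fall in one arm and rest on cGFR inputs chosen for illustration. The scoring error does not depend on those inputs; whether it arises depends on at least one loss or death before an observed Month 3 value. Absolute cGFR summaries and the change scores of losses after Month 3 are unaffected.

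**What to change.** In SAP 7.6.2.3 and 8.3:

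1. State that zero imputation applies to the absolute cGFR summaries and to visits after Month 3, but not to Month 3 when it serves as reference or covariate.
2. Restrict the change and slope analyses to subjects with an observed Month 3 cGFR. Label them conditional on a functioning graft at Month 3, and report by arm how many were excluded for earlier loss or death.
3. Record the departure from Protocol 8.4.2.3 in SAP 7.1.
4. Present the change contrast beside the absolute cGFR summaries with zeros, because step 2 removes the early losses from the contrast (shift about 0). A supportive between-arm model of absolute cGFR with zeros and without the Month 3 covariate is optional. In the illustration it shows the losses (about -4.4 for three) but is imprecise (SE 4.3 to 5.3).

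No new data are needed. The price is that a few subjects may leave the change and slope analyses, which then describe only those who reach Month 3 alive with a functioning graft. That is a condition set after randomisation, and it must be stated.

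### The SAP fits the cGFR slope and repeated-measures models with zeros after graft loss or death, and no visible companion analysis shows them without the zeros

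*SAP*

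**What the plan says.** Protocol section 8.4.2.3 puts the zero rule directly after the descriptive summaries ("For a subject who has one or more missing values for cGFR due to a graft loss or death"). It then announces a linear mixed effects model and leaves the details to the SAP. It does not say whether the rule reaches that model.

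SAP section 7.6.2.3 specifies three cGFR analyses:

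- descriptive summaries;
- a repeated-measures model for change from Month 3, with month categorical and an arm difference with 95% CI at each visit;
- a slope model with month continuous, giving a mean slope with 95% CI for each arm.

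Of the slope model it says "The model will also include a random intercept and slope for month". Table 7.6.2.3-1 gives its outcome as "Analysis on absolute cGFR value using Month 3 cGFR as a covariate", at Months 6, 12 and 24. Month 3 is therefore a predictor and not an outcome. The zero rule follows, introduced by "For all of the analyses above, for any subject who has one or more missing values for cGFR".

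SAP section 8.3 repeats the rule as a general convention: "Missing cGFR values due to death or graft loss will be imputed with value of 0 and all other missing values will remain missing". SAP section 7.1, which lists the changes from the protocol's analyses, does not mention it. In the unredacted text, no cGFR model omits the zeros or is restricted to functioning grafts.

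**The concern.** Slope of cGFR and change from Month 3 are listed secondary endpoints for renal function, separate from subject and graft survival. A subject whose graft is lost after Month 12 enters the slope model as, for example, 60, 60, 0. That is a step rather than a gradual decline, and it lies far outside the spread of the other 34 subjects. A straight-line, normal-theory model turns it into a steeper mean slope and a larger variance. A death with a functioning graft enters in the same way as a failed graft.

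Two features of this trial make that matter. No tests are planned, so the estimates and intervals are the result. And under SAP sections 7.1 and 7.6.2.1, fewer than five deaths or graft losses across both arms means that survival is listed but not summarized. The zeros enter the cGFR models all the same, so a reader could take a slope driven partly by one or two losses for the rate at which working grafts decline.

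**Working it through.** **Inputs from the documents.** 35 per arm; slope outcomes at Months 6, 12 and 24; zeros after loss; two-sided 95% intervals; one unstructured covariance, with no separate structure by arm. The plan states no precision figure for cGFR, so there is none to reproduce.

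**Assumptions (not in the documents).** cGFR level 60, range 45 to 70; true slope -1.5 per year; between-subject slope SD 3; visit SD 5; residual SD of change 10; zero, one or two losses, all in one arm. Slopes are in mL/min/1.73m² per year.

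**1. Slope of one affected subject.** The visit times average 14 months, with deviations -8, -2 and +10 and sum of squares 168. At cGFR 60:

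- loss between Months 12 and 24 (60, 60, 0): 12 × (-8×60 - 2×60)/168 = -42.9;
- loss between Months 6 and 12 (60, 0, 0): 12 × (-8×60)/168 = -34.3;
- loss before Month 6 (0, 0, 0): 0.

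**2. Shift in the arm mean: divide by 35.**

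| cGFR level | Loss at Months 6–12 | Loss at Months 12–24 |
|---|---|---|
| 45 | -0.73 | -0.92 |
| 60 | -0.98 | -1.22 |
| 70 | -1.14 | -1.43 |

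**3. Arm mean slope with a true slope of -1.5.** Starting from 60 at Month 3, the values are 59.6 at Month 6 and 58.9 at Month 12. A subject lost after Month 12 then has slope -42.5.

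- One loss: (34 × -1.5 - 42.5)/35 = -2.7. The zeros supply 1.2 of 2.7, or 44%.
- Two losses: (33 × -1.5 - 85.0)/35 = -3.8. The zeros supply 2.3 of 3.8, or 61%.

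**4. Per-arm half-width with pooled variance.** The per-subject slope variance is 3² + 5²/(168/144) = 30.4. A lost subject lies about 41 from the others (42.5 - 1.5). With k losses in one arm, the pooled variance (68 df) rises by k(35-k)/35 × 41²/68, which is 24.0 for one and 46.6 for two.

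- None: 1.995 × √(30.4/35) = 1.86.
- One: 1.995 × √(54.4/35) = 2.49.
- Two: 1.995 × √(77.0/35) = 2.96.

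A simulation of 4,000 trials on the same assumptions, using averaged per-subject slopes and pooled variance, gives 1.85, 2.50 and 2.98.

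**5. Month 24 contrast.** The model is taken as change from Month 3 adjusted for Month 3, with residual SD 10 and a zero about 60 from the rest. The residual variance becomes 100 + k(35-k)/35 × 60²/67, which is 100, 152 and 201.

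- Half-width, 1.996 × √(variance × 2/35): 4.8, 5.9 and 6.8.
- Shift in the point difference per unbalanced loss: 60/35 = 1.7.

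**6. The SAP's slope model fitted directly.** Thirty-one simulated trials were fitted by REML with random intercept and slope. The assumptions differed: mean 57, between-subject SD 16, within-subject SD 7, true slope -1 with SD 2.5. The Month 24 column is an analysis of covariance standing in for that visit of the repeated-measures model. With so few trials the figures are approximate.

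| Losses after Month 12 | Arm slope | Half-width, slope difference | Half-width, Month 24 |
|---|---|---|---|
| None | -0.57 | 3.26 | 4.93 |
| One, as zero | -1.66 | 3.89 | 5.85 |
| Two, as zero | -2.87 | 4.72 | 6.84 |
| One, left missing | -0.52 | 3.28 | 4.97 |
| Two, left missing | -0.47 | 3.30 | 5.02 |

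One or two losses before Month 6 leave the slope at -0.51 and -0.44. They still widen the Month 24 interval to 5.85 and 6.84. With equal late losses in both arms (1+1, 2+2) the slope difference stays at -0.25 and -0.20, against -0.25 with none. Its half-width rises to 4.56 and 5.68.

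**The case against.** The strongest reply is that zero for a lost graft is a legitimate composite strategy, that the rule comes from the protocol, and that nothing is decided on it. The study is descriptive and unpowered. All deaths and graft losses are listed whatever their number, so a reader can identify the zeros, and median cGFR, which one or two zeros barely move, is planned beside the mean. The alternative without zeros conditions on graft survival and so has its own weakness. All of this stands. It argues for keeping the planned analyses and keeps the priority modest. It does not supply a slope that describes functioning grafts, because the planned median concerns visit values and the listings do not alter the fitted models.

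Three stronger readings that a reader might reach are not supported:

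- **That the SAP overrides the protocol.** The protocol's sentence has no scope limit, and its synopsis puts the rule immediately before the model. The SAP settles an open question.
- **That any loss after Month 3 steepens the slope.** A loss between Months 3 and 6 enters as 0, 0, 0 and leaves the slope essentially unchanged. It affects the repeated-measures contrasts only.
- **That the zeros inflate the treatment difference.** They widen its interval. The point difference can grow, shrink or stay put, depending on which arm has the losses.

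**Conclusion.** The concern holds in a limited form. SAP section 7.6.2.3 carries the zeros into both cGFR models, and no visible analysis shows what the models give without them. Each loss after Month 6 moves the arm mean slope by -0.7 to -1.4 per year. That range needs only 35 per arm and an assumed cGFR of 45 to 70.

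The other figures rest on assumed variability, slope and loss counts, none of which the documents give. On those assumptions the per-arm slope half-width rises by about 35% with one late loss and 60% with two. The Month 24 half-width rises from about 4.9 to 5.9 and 6.8. The Month 24 point difference shifts by 1.6 to 1.7 per unbalanced loss, which is well inside that half-width.

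It would go too far to say that a single loss always dominates the slope. With a true slope of -1.5 it supplies somewhat under half of the estimate, and only two losses pass half. With a flatter underlying slope, as in the direct model fits, one loss supplies about two thirds. No test or decision turns on this. What is at stake is whether the reported slope can be read as renal function.

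**What to change.** Keep the zero-imputed summaries and both planned models as they are. Add to SAP section 7.6.2.3 that the slope model and the repeated-measures model will also be fitted on cGFR values observed with a functioning graft, with values after loss or death left missing. Report the two versions together, with the number of deaths and graft losses in each arm even when there are fewer than five overall. State that the no-zero slope is the rate of change in functioning grafts and that the zero-imputed slope also reflects graft loss and death.

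The cost is a few sentences in the SAP and one re-run of two models on data already collected. No protocol amendment is needed. The downside is that the no-zero result is conditional on survival with a functioning graft and could flatter an arm with more losses. It must therefore not be shown without the zero-imputed result beside it.
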